5.3.5 Neurologic Toxicity

Arsenic trioxide may cause neuropathy which most commonly involves painful peripheral neuropathy. This should be managed with medications appropriate for neuropathy (such as gabapentin or pregabalin) and pain medication (including narcotics as needed). Arsenic trioxide dosing should be modified for Grade ≥ 3 neuropathy by following the guidelines in Section 5.3.6 below.

5.3.6 Other Toxicities (Excludes hepatic, hematologic, nausea/vomiting, and cardiac toxicities which are described above)

If a patient has active vasomotor symptoms during the infusion (including dizziness, hypotension, tachycardia, or flushing) the infusion time may be extended to 4 hours.

If a patient experiences a Grade ≥ 3 toxicity that is felt to be related to arsenic trioxide, arsenic trioxide will be held until the toxicity has resolved to Grade ≤ 1 . At that time restart arsenic trioxide at a 75% dose (0.11 mg/kg/day). Recurrent episodes of Grade ≥ 3 toxicity will result in holding of arsenic trioxide until the toxicity resolves to Grade ≤ 1 ; arsenic trioxide will then be resumed with an additional 25% reduction in the arsenic trioxide dose (0.075 mg/kg/day). Patients experiencing Grade ≥ 3 toxicity attributable to arsenic trioxide while on 0.075 mg/kg/day of arsenic trioxide should be discussed with the study chair.

5.4 **IDArubicin and MitoXANtrone Dose Modifications**

5.4.1 Hepatic Toxicity

IDArubicin

Dose Adjustments for IDArubicin		
Direct Bilirubin	BSA $\geq 0.6m^2$	BSA $< 0.6m^2$
< 2.6 mg/dL	100% dosing (12 mg/m ² /dose)	100% dosing (0.4 mg/kg/dose)
2.6-5 mg/dL	50% dosing (6 mg/m ² /dose)	50% dosing (0.2 mg/kg/dose)
> 5 mg/dL	Hold until direct bilirubin < 5 mg/dL	Hold until direct bilirubin < 5 mg/dL

If held for direct bilirubin > 5 mg/dL, start (or restart) IDArubicin doses once the direct bilirubin falls below 5 mg/dL (give at 50% dose if the direct bilirubin is 2.6 - 5 mg/dL or give at full dose if direct bilirubin is < 2.6 mg/dL). Although the doses may be delayed, **all high risk patients should still receive a total of 4 IDArubicin doses** (each dose may be either full dose or reduced dose) spaced at least 48 hours apart during Induction. Please notify the study chair of patients who require delays in IDArubicin doses due to direct hyperbilirubinemia in Induction

MitoXANtrone

Dose Adjustments for MitoXANtrone		
Direct Bilirubin	BSA \geq 0.6m²	BSA < 0.6m²
< 3.4 mg/dL	100% dosing (12 mg/m ² /dose)	100% dosing (0.4 mg/kg/dose)
3.4-5 mg/dL	25% dosing (3 mg/m ² /dose)	25% dosing (0.1 mg/kg/dose)
> 5 mg/dL	Hold until direct bilirubin < 5 mg/dL	Hold until direct bilirubin < 5 mg/dL

In severe liver dysfunction, the half-life of mitoXANtrone is prolonged and the AUC may be more than 3 fold that of patients with normal hepatic function. If the direct bilirubin is > 5 mg/dL, hold the mitoXANtrone dose. If the direct bilirubin is between 3.4 and 5 mg/dL, give 25% of the mitoXANtrone dose. Monitor the direct bilirubin closely and if it decreases to < 3.4 mg/dL, further doses of mitoXANtrone may be given at full dose.

5.4.2 Renal Toxicity

If creatinine clearance (CrCl) < 50 mL/minute, administer 75% of the IDArubicin dose (if BSA < 0.6 m², 0.3 mg/kg/dose, if BSA \geq 0.6 m², 9 mg/m²/dose).

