3.2.1 Age

Patient must be ≥ 12 months and < 22 years of age at first diagnosis of APL.

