4.8.2 Required Observations in Induction – High Risk APL

All baseline studies must be performed prior to starting protocol therapy unless otherwise indicated below. Obtain other studies during Induction as indicated.

- | |
|--|
| 
 a. History b. Physical Exam with VS: weekly c. Ht, Wt, BSA: Days 1, 29 and 57 d. Performance status e. Pregnancy test: Female patients of childbearing potential require a negative pregnancy test prior to starting treatment; sexually active patients must use an acceptable method of birth control. f. CBC, differential, platelets: daily during Week 1, then at least once weekly g. Urinalysis h. Electrolytes including Ca⁺⁺, Mg⁺⁺, K⁺ and creatinine: daily during Week 1, then at least once weekly i. Uric Acid j. AST, ALT, Total Bilirubin (and Direct Bilirubin if Total Bilirubin is >2 mg/dL): Once weekly k. Cholesterol triglycerides l. PT, PTT, fibrinogen, D-Dimer: daily during Week 1, then on Days 8, 15 and 29 (more frequently if needed for active coagulopathy) m. ECG for QTc monitoring: Weekly n. Echocardiogram or MUGA o. BMA for morphology: At diagnosis and Day 29 and every 2 weeks thereafter as needed until hCR/hCRi p. BMA for flow cytometry, cytogenetics & FISH: At diagnosis q. BMA for clinical RQ-PCR of PML-RARα: At diagnosis. This clinical testing is separate from research samples submitted for the optional MRD RQ-PCR study; this mandatory clinical testing is not free of charge and the cost is not covered by the study, but the specimen must be sent to one of the approved labs for PML-RARα RQ-PCR testing; a list of approved labs is available on the protocol-specific web page of the COG website. r. FLT3 (optional)*: bone marrow (or peripheral blood if bone marrow is unavailable) at diagnosis. See Section 15.1 for details. s. Research MRD (optional)*: bone marrow and peripheral blood at diagnosis and Day 29 of Induction. See Section 15.2 for details. Results of this research testing will not be returned to sites. This research testing does not take the place of the mandatory RQ-PCR clinical testing that must be done at the time of initial diagnosis (see observation “q” above). t. Coagulopathy (optional)*: peripheral blood at diagnosis (if available), Day 1, Day 8, Day 15 and Day 29 of Induction. See Section 15.3 for details. |
|--|

*Only obtain in patients who have consented to participation in this component of the trial.

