Note: If the patient received pre-treatment with ATRA prior to starting Day 1 of protocol directed therapy (see [Section 3.2.3](#)), these pre-treatment doses are NOT considered part of the required 28 days minimum of induction protocol therapy.

Arsenic Trioxide (ATO): IV daily over 2 hours (may lengthen infusion to 4 hours if active vasomotor symptoms occur)

Days: 1 - 28 minimum. Continue beyond day 28 if not in hCR/hCRi up to a maximum of 70 days (See [Section 10.2](#) for response criteria and definition of hCR/hCRi)

Dose: 0.15 mg/kg/day (no maximum dose)

IDArubicin: IV bolus over 15 minutes

Days: 1, 3, 5, 7

Dose: 12 mg/m²/dose, once a day

NOTE: if BSA < 0.6 m², 0.4 mg/kg/dose

Dexamethasone: PO/IV BID

Days: 1 - 14

Dose: 2.5 mg/m²/dose twice daily. The total daily dose is 5 mg/m²/day.

Note: This is prophylaxis dosing of dexamethasone. If the patient develops actual symptoms of differentiation syndrome, refer to [Section 5.1](#) for recommendations on diagnosis and management of differentiation syndrome including treatment dosing of dexamethasone.

Indications for intrathecal therapy

CNS Bleed

Patients with documented CNS bleed will receive CNS prophylaxis to include triple intrathecal chemotherapy at Day 29 of Induction. See table below for age-based dosing.

CNS Disease

Patients with CNS disease (see [Section 3.3.4](#) for definition) will receive twice weekly triple intrathecal chemotherapy (with a minimum interval of 48 hours between treatments) until the CSF is cleared plus two additional twice weekly treatments (minimum of 4 and maximum of 6 treatments). During Induction, patients with CNS disease will also receive a 10 mg/m² dose of leucovorin, 24 hours after each of the twice weekly triple intrathecal therapies.

Age-based dosing of triple intrathecal therapy:

Age	Triple Intrathecal Therapy (ITT)		
	Methotrexate	Hydrocortisone	Cytarabine
1 - 1.99 years	8 mg	15 mg	30 mg
2 - 2.99 years	10 mg	25 mg	50 mg
≥ 3 years	12 mg	35 mg	70 mg

See [Section 5.0](#) for Dose Modifications based on Toxicities.

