5.5.2 Renal Toxicity

Patients with nephrotoxicity secondary to antibiotics, or antifungals, may have prolonged excretion of cytarabine leading to more severe marrow and extramedullary toxicity. Patients with a serum creatinine > 2 mg/dL or > 2 x upper limit of normal for age should be hydrated orally or intravenously. Following hydration, the patient must have a creatinine clearance \geq 60 mL/min/1.73m² as measured preferably by a nuclear GFR scan, timed urine collection for creatinine clearance, or calculated by the IDMS-traceable Schwartz equation for children⁶⁸ or the IDMS-traceable MDRD study equation for adults⁶⁹ (see equations below) before proceeding with HD cytarabine therapy (doses of 1 g/m²). If the CrCl is abnormal (< 60 mL/min/1.73m²) then high dose cytarabine should be reduced from twice daily to once daily dosing, at the same previously prescribed doses (i.e., 50% daily dose reduction if BSA < 0.6 m², 33.3 mg/kg/day, if BSA \geq 0.6 m², 1,000 mg/m²/day). With this approach, previous research has shown the prevention

of subsequent neurotoxicity in recipients of high dose cytarabine in the face of renal insufficiency.⁷⁰

For patients < 18 years old:

GFR (in mL/min/1.73 m²) = (0.41 x Height in cm)/(serum creatinine in mg/dL)

Online calculator **for patients < 18 years old** available at:

<http://nkdep.nih.gov/lab-evaluation/gfr-calculators/children-conventional-unit.asp>

For patients ≥ 18 years old:

GFR (in mL/min/1.73 m²) = 175 x (serum creatinine in mg/dL)^{-1.154} x (Age in years)^{-0.203} x (0.742 if female) x (1.212 if African American)

Online calculator **for patients ≥ 18 years old** available at:

<http://nkdep.nih.gov/lab-evaluation/gfr-calculators/adults-conventional-unit.asp>

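### The idarubicin renal limit in Section 5.4.2 is an absolute 50 mL/minute, so as printed it cuts the dose for a small child with normal kidneys

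*Combined protocol and SAP*

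**What the plan says.** The idarubicin renal rule in Section 5.4.2 reads: "If creatinine clearance (CrCl) < 50 mL/minute, administer 75% of the IDArubicin dose". It then gives the reduced dose in two branches. The one for small children is "if BSA < 0.6 m², 0.3 mg/kg/dose"; the other is 9 mg/m² per dose. No measurement method is named and no other section is referred to.

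The full doses are in Section 4.8.3: "12 mg/m²/dose, once a day", with the exception "NOTE: if BSA < 0.6 m², 0.4 mg/kg/dose". Idarubicin is given on Days 1, 3, 5 and 7 of Induction, to high-risk patients only.

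The only other clearance-based dose rule is for cytarabine, in Section 5.5.2: "If the CrCl is abnormal (< 60 mL/min/1.73m²) then high dose cytarabine should be reduced from twice daily to once daily dosing". That section lists acceptable methods (nuclear GFR, timed urine collection, or an equation). Its equation for patients under 18 is "GFR (in mL/min/1.73 m²) = (0.41 x Height in cm)/(serum creatinine in mg/dL)", and its adult equation returns the same unit.

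Small children are a planned case. Section 3.2.1 states: "Patient must be ≥ 12 months and < 22 years of age at first diagnosis of APL". For monitoring in high-risk Induction, Section 4.8.2 requires "creatinine: daily during Week 1, then at least once weekly", and height on Day 1. It does not require a calculated or measured clearance.

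**The concern.** Absolute clearance in mL/minute scales with body size; clearance per 1.73 m² does not. A fixed absolute limit therefore becomes stricter as the child gets smaller, and the 5.4.2 rule has a dose branch for exactly the children in whom the two units differ most. Nothing in the documents says that the limit is to be read as indexed.

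Two things are at stake. First, a rule meant for renal toxicity would, followed as printed, remove a quarter of each idarubicin dose from a small child whose kidneys are normal. Idarubicin is what separates high-risk from standard-risk Induction. Section 2.6 gives its purpose as lowering relapse risk and the white count, and Section 5.4.1 insists that every high-risk patient still receive all four doses. Second, two sites could apply the same sentence differently to the same child: one in the printed unit, one by comparing the output of the 5.5.2 equation with 50.

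The rule cannot be treated as dormant. Section 3.2.4.4 excludes only patients with creatinine above 3.0 mg/dL or on active dialysis, so patients with impaired kidneys can enroll and sites need a usable limit.

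**Working it through.** **The plan's own figures.** 75% of 0.4 mg/kg is 0.75 × 0.4 = 0.3 mg/kg, and 75% of 12 mg/m² is 0.75 × 12 = 9 mg/m². Both match Section 5.4.2, so the reduced doses are right. The question is only when they apply.

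**Conversion.** Absolute clearance = indexed GFR × BSA / 1.73. The indexed value equivalent to 50 mL/minute is therefore 50 × 1.73 / BSA.

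| BSA (m²) | Indexed equivalent of 50 mL/min | Absolute clearance at indexed GFR 90 | at 120 | at 140 |
|---|---|---|---|---|
| 0.40 | 216.2 | 20.8 | 27.7 | 32.4 |
| 0.50 | 173.0 | 26.0 | 34.7 | 40.5 |
| 0.60 | 144.2 | 31.2 | 41.6 | 48.6 |
| 1.73 | 50.0 | 90.0 | 120.0 | 140.0 |

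The 90–140 range is an assumption. Over all of it, every child at or below 0.6 m² falls under 50 mL/minute. The result does not depend closely on the range: below 0.6 m², any indexed GFR up to about 144 triggers the reduction.

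**How far the effect reaches.** The BSA below which a given indexed GFR falls under 50 mL/minute is 50 × 1.73 / GFR:

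- GFR 90: 0.96 m²
- GFR 100: 0.87 m²
- GFR 120: 0.72 m²
- GFR 140: 0.62 m²

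**Opposite direction.** At 2.2 m² the indexed equivalent is 50 × 1.73 / 2.2 = 39.3. A patient of that size with an indexed GFR between about 39 and 50 would escape a reduction that an indexed limit would require.

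**Worked child** (assumed 87 cm, 12.5 kg). Mosteller BSA = √(87 × 12.5 / 3600) = 0.55 m². With the Section 5.5.2 equation for patients under 18:

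- Creatinine 0.3 mg/dL: indexed GFR = 0.41 × 87 / 0.3 = 118.9; absolute = 118.9 × 0.55 / 1.73 = 37.8. As printed, the dose is 0.3 × 12.5 = 3.75 mg; with an indexed limit it is 0.4 × 12.5 = 5.0 mg. Over four doses, 15 mg against 20 mg.
- Creatinine 0.2 mg/dL: indexed 178.3, absolute 56.7. Both readings give the full dose.
- Creatinine at which the reduction starts: as printed, 0.41 × 87 / (50 × 1.73 / 0.55) = 0.23 mg/dL; with an indexed limit, 0.41 × 87 / 50 = 0.71 mg/dL.

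**Rough count.** Section 16.4.1 reports 6 eligible participants (5%) under 5 years on the preceding trial, AAML0631, apparently over both risk groups. If the high-risk group here has the same age mix (an assumption), 5% of the 54 planned patients is 0.05 × 54 = 2.7, about 3 children under 5, and fewer below 0.6 m². The reach beyond 0.6 m² could add some older children, mainly at the lower end of the GFR range.

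**The case against.** The strongest reply is that the harm needs a step the protocol never prescribes. Sites must collect creatinine, not clearance. The only formulas printed for turning one into the other are in Section 5.5.2, and both give an indexed value. A site that sets that value against 50 gives the full dose to every child with an indexed GFR of 90–140. To reach 75%, someone must convert back by BSA/1.73, or obtain a timed urine clearance reported without indexing. Nor does anything direct a site to calculate clearance in a child with unremarkable creatinine; the rule sits among modifications for toxicity. For small children the consequence is a 25% lower dose of one drug while ATRA and ATO continue. Section 6.0 also sends sites to drug monographs that could not be seen, so whether 50 was meant as absolute or indexed is not known.

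Much of this stands. It shows that under-dosing is not the certain or even the usual result, and it limits the scale. It does not remove the defect. The site that goes wrong in this account is the one that follows the printed unit, and the site that doses sensibly does so by disregarding it. A dosing rule in the protocol should not need an outside document to supply its unit.

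**Conclusion.** The concern holds as a minor point. The unit in 5.4.2 conflicts with the only other clearance rule in the protocol, nothing reconciles them, and the printed form gives the wrong answer for the small children whom the sentence itself provides for. Read as printed, it withholds 25% of each of four idarubicin doses from a child below 0.6 m² with an indexed GFR up to about 144. Not every small child is affected, as the creatinine 0.2 mg/dL case shows.

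Confidence is high for the unit mismatch and the arithmetic. How often a dose would actually be cut depends on site practice, which the documents do not show. The illustration rests on an assumed normal GFR of 90–140 and an assumed child. The number of affected patients is not in the documents but is likely to be very small, and no material effect on the high-risk EFS analysis is shown.

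**What to change.** In Section 5.4.2, state the limit as CrCl < 50 mL/min/1.73 m² and refer to the measurement methods and equations in Section 5.5.2. The sponsor's clinical team should confirm that an indexed limit was intended. If an absolute limit was meant, the text should say so and justify it for children below 0.6 m².

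The cost is one changed unit and one cross-reference. No new test is needed: creatinine is already required daily in Week 1, which covers all four idarubicin days, and height is recorded on Day 1. The sample size and the analysis are unchanged.

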5.4.3 Left Ventricular Cardiac Function Toxicity

IDArubicin and mitoXANtrone will be withheld if there is significant evidence of cardiac disease by echocardiogram or MUGA (shortening fraction < 27%). Do not re-start these drugs if withheld for this reason.

5.5 **Cytarabine Dose Modifications**5.5.1 Neurological Toxicity

Patients with Grade \geq 3 neurotoxicity from high dose cytarabine should not receive further high dose cytarabine. The most common neurotoxicity is an acute cerebellar syndrome that may manifest itself as ataxia, nystagmus, or dysarthria. However, seizures and encephalopathy have also occurred following therapy with high dose cytarabine.

5.5.2 Renal Toxicity

Patients with nephrotoxicity secondary to antibiotics, or antifungals, may have prolonged excretion of cytarabine leading to more severe marrow and extramedullary toxicity. Patients with a serum creatinine > 2 mg/dL or > 2 x upper limit of normal for age should be hydrated orally or intravenously. Following hydration, the patient must have a creatinine clearance \geq 60 mL/min/1.73m² as measured preferably by a nuclear GFR scan, timed urine collection for creatinine clearance, or calculated by the IDMS-traceable Schwartz equation for children⁶⁸ or the IDMS-traceable MDRD study equation for adults⁶⁹ (see equations below) before proceeding with HD cytarabine therapy (doses of 1 g/m²). If the CrCl is abnormal (< 60 mL/min/1.73m²) then high dose cytarabine should be reduced from twice daily to once daily dosing, at the same previously prescribed doses (i.e., 50% daily dose reduction if BSA < 0.6 m², 33.3 mg/kg/day, if BSA \geq 0.6 m², 1,000 mg/m²/day). With this approach, previous research has shown the prevention

of subsequent neurotoxicity in recipients of high dose cytarabine in the face of renal insufficiency.⁷⁰

For patients < 18 years old:

GFR (in mL/min/1.73 m²) = (0.41 x Height in cm)/(serum creatinine in mg/dL)

Online calculator **for patients < 18 years old** available at:

<http://nkdep.nih.gov/lab-evaluation/gfr-calculators/children-conventional-unit.asp>

For patients ≥ 18 years old:

GFR (in mL/min/1.73 m²) = 175 x (serum creatinine in mg/dL)^{-1.154} x (Age in years)^{-0.203} x (0.742 if female) x (1.212 if African American)

Online calculator **for patients ≥ 18 years old** available at:

<http://nkdep.nih.gov/lab-evaluation/gfr-calculators/adults-conventional-unit.asp>

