ATRA  (further daily doses if not hCR/hCRi on Day 29 bone marrow)

ATO  (further daily doses if not hCR/hCRi on Day 29 bone marrow)

[figure not shown]
Dex 

Ida **X X X X**

(Ida= Idarubicin given on Days 1, 3, 5, 7)

Consolidation:

Standard Risk and High Risk APL

(*Only if Week 14 RQ-PCR of PML-RAR α positive, repeat testing in 1-2 weeks. If repeat test is confirmed positive continue to MRD Positive Consolidation)

See the Chemotherapy Administration Guidelines (CAG) for children on the COG website at:

https://cogmembers.org/_files/disc/Pharmacy/ChemoAdminGuidelines.pdf for special precautions and suggestions for patient monitoring. As applicable, also see the CAG for suggestions on hydration, or hydrate according to institutional guidelines.

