4.5.2 Required Observations in MRD Positive Consolidation – Standard Risk APL

- | |
|--|
| 
 a. Physical Exam with VS: every 4 weeks b. Ht, Wt, BSA c. CBC, differential, platelets: Weekly d. Electrolytes and creatinine: Weekly e. AST, ALT, Total Bilirubin (and prior to Mitoxantrone a Direct Bilirubin if Total Bilirubin is >3.3 mg/dL): Weekly f. Cholesterol, triglycerides g. Echocardiogram or MUGA h. BMA for mandatory clinical RQ-PCR of PML-RARα: Obtain on Day 29. If sample is positive, repeat 1 - 2 weeks later. This testing is not paid for by the study. It is recommended that this testing be sent to either Hematologies, Inc, Seattle, WA, USA or the Molecular Haematology Lab, Royal Prince Alfred Hospital, NSW, Australia due to their experience with these samples. |
|--|

This table only includes evaluations necessary to answer the study aims. Obtain other studies as indicated for good clinical care.

Comments

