4.5.3 MRD Positive Consolidation Treatment Details – Standard Risk APL

MRD Positive Consolidation consists of a combination of high dose cytarabine, mitoxantrone and twice daily ATRA. This cycle lasts for 28 days. It is strongly recommended that the patients remain inpatient for the duration of this cycle of Consolidation and until count recovery.

Antifungal prophylaxis should be strongly considered (dependent on institutional practice) during this cycle due to an expected prolonged period of neutropenia. However, treating physicians should be aware that azole antifungal medications may increase ATRA toxicity due to inhibition of cytochrome P - 450 metabolism of ATRA. Thus patients should be monitored closely for adverse events such as, pseudotumor cerebri or renal dysfunction, during periods of concomitant use. For prophylactic antifungal use, initiation of an azole antifungal could be delayed until after completion of ATRA on Day 14 of this cycle or an alternate non-azole antifungal should be considered.

High Dose Cytarabine: IV over 1 - 3 hours every 12 hours

Days: 1 - 4 (8 total doses)

Dose: 1,000 mg/m²/dose every 12 hours. If BSA < 0.6 m², 33.3 mg/kg/dose.

NOTE: Administer steroid eye drops (0.1% dexamethasone or 1% prednisolone ophthalmic solution), 2 drops to each eye every 6 hours, beginning immediately before the first dose and continuing for 24 hours after the final dose. If patient does not tolerate steroid eye drops, may administer artificial tears on an every 2 - 4 hour schedule.

MitoXANtrone: IV daily over 15 - 30 minutes

Days: 3 - 6

Dose: 12 mg/m²/dose once daily. If BSA < 0.6 m² 0.4 mg/kg/dose.

Administer through the tubing of a rapidly infusing solution of D₅W or 0.9% NaCl. Avoid extravasation; the use of a central line is suggested. On Days 3 and 4, mitoxantrone should be given 8 hours after the 5th and 7th high dose cytarabine infusions are complete.

Tretinoin (ATRA): PO divided BID

Days: 1 - 14

Dose: 12.5 mg/m²/dose, twice daily. The total dose is 25 mg/m²/day divided twice daily.

Administer with food. Refer to [Appendix II](#) for dosing table (includes dose recommendations for very young patients).

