6.0 DRUG INFORMATION

See the consent document for toxicities. All other information is available on the COG website in the commercial agent monographs manual titled “Drug Information for Commercial Agents used by the Children’s Oncology Group.” On the COG website, this manual is provided under Standard Sections for Protocols

at: https://www.cogmembers.org/site/pages/default.aspx?page=Prot_reference_materials

Please see [Appendix IV](#) for drug interactions associated with the drugs used in this study.

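### Section 5.5.2 halves daily high dose cytarabine at clearance below 60, but its creatinine trigger for checking clearance can miss patients already below 60

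*Combined protocol and SAP*

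**What the plan says.** High dose cytarabine is given only in MRD Positive Consolidation: eight doses over Days 1 to 4 (Sections 4.5.3 and 4.11.3). Section 5.5.2 sets the renal rule in three steps.

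- Trigger: "Patients with a serum creatinine > 2 mg/dL or > 2 x upper limit of normal for age should be hydrated orally or intravenously".
- Check: "Following hydration, the patient must have a creatinine clearance" of at least 60 mL/min/1.73 m² before treatment proceeds. It may be measured (preferred) or calculated from a printed equation.
- Action: if clearance is below 60, "then high dose cytarabine should be reduced from twice daily to once daily dosing", which halves the daily dose. The stated reason is prevention of neurotoxicity in renal insufficiency.

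The under-18 equation is printed as ("0.41 x Height in cm)/(serum creatinine in mg/dL"). A second equation, for 18 years and over, uses creatinine, age, sex and a race factor.

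The required observations for this cycle (Sections 4.5.2 and 4.11.2) list "Electrolytes and creatinine: Weekly" and no clearance or GFR. The therapy delivery maps (4.5.1 and 4.11.1) schedule creatinine on Day 1 and next on Day 8. For further precautions the protocol points outside itself. Section 4.1 sends sites to the Chemotherapy Administration Guidelines "for special precautions and suggestions for patient monitoring", and Section 6.0 says: "All other information is available on the COG website in the commercial agent monographs manual".

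**The concern.** The action threshold is a clearance and the screening threshold is a creatinine. The screen does its job only if every patient with clearance below 60 also exceeds the creatinine trigger. For a wide range of ULN values that is not so: GFR falls below 60 at a creatinine well under the trigger.

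A patient in between need not have clearance determined under the protocol text, and so can be given the full twice-daily schedule. Day 1 is the only scheduled creatinine before the eight doses are finished. At stake is neurotoxicity, which Section 5.5.1 describes as cerebellar syndrome, seizures and encephalopathy. This is a patient-safety point and does not touch the analysis of EFS.

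**Working it through.** The plan states no GFR at the trigger, so there is no figure of its own to reproduce. The check evaluates the equations in 5.5.2 at the trigger.

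**Inputs from 5.5.2.** Trigger: creatinine above the lower of 2 mg/dL and 2 × ULN for age. Action threshold: 60 mL/min/1.73 m². Equations:

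- Under 18: GFR = 0.41 × height / creatinine.
- 18 and over: GFR = k × creatinine^−1.154, with k = 175 × age^−0.203, times 0.742 if female, times 1.212 for the race factor.

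**Assumptions.** The documents give neither ULN nor heights, so both are varied.

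**Step 1: creatinine at which GFR reaches 60.** Under 18 this is 0.41 × height / 60: 0.68 mg/dL at 100 cm, 0.82 at 120, 0.96 at 140, 1.09 at 160, 1.16 at 170 and 1.30 at 190. At 18 to 21 it is (k/60)^(1/1.154). For a man of 18 without the race factor, k = 97.3 and the result is 1.52. Over ages 18 to 21, with and without the race factor, the range is 1.14 to 1.39 for women and 1.48 to 1.80 for men.

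**Step 2: GFR at the trigger T = min(2, 2 × ULN), under 18.**

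| Assumed ULN | T | 140 cm | 160 cm | 170 cm | 190 cm |
|---|---|---|---|---|---|
| 0.5 | 1.0 | 57.4 | 65.6 | 69.7 | 77.9 |
| 0.6 | 1.2 | 47.8 | 54.7 | 58.1 | 64.9 |
| 0.8 | 1.6 | 35.9 | 41.0 | 43.6 | 48.7 |
| 1.0 or more | 2.0 | 28.7 | 32.8 | 34.9 | 39.0 |

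For example, 0.41 × 140 / 2 = 28.7. In shorter children (100 / 120 cm): 51.2 / 61.5 at ULN 0.4, and 41.0 / 49.2 at ULN 0.5. Any value below 60 means a gap.

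**Step 3: the same for ages 18 to 21.** Each range runs over age; the second column applies the race factor.

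| Sex, assumed ULN | Without | With |
|---|---|---|
| Women, 0.6 | 56.7–58.5 | 68.7–70.9 |
| Women, 0.8 | 40.7–42.0 | 49.3–50.9 |
| Women, 1.0 or more | 31.5–32.5 | 38.1–39.3 |
| Men, 0.8 | 54.8–56.6 | 66.5–68.6 |
| Men, 0.9 | 47.9–49.4 | 58.0–59.9 |
| Men, 1.0 or more | 42.4–43.7 | 51.4–53.0 |

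**Step 4: ULN at which the gap closes.** Setting 2 × ULN equal to the Step 1 creatinine gives, under 18, ULN = 0.41 × height / 120, about 0.0034 × height: 0.34 at 100 cm, 0.48 at 140, 0.58 at 170 and 0.65 at 190. At 18 to 21 it is 0.57 to 0.69 for women and 0.74 to 0.90 for men.

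**Step 5: an example inside the gap.** A patient under 18, 160 cm tall, with creatinine 1.5 and ULN 0.8: the trigger is 1.6 and is not met, yet GFR = 65.6 / 1.5 = 43.7.

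**Step 6: dose at stake (BSA 0.6 m² or more).** Twice daily: 8 × 1,000 = 8,000 mg/m² over Days 1 to 4. Once daily: 4 × 1,000 = 4,000 mg/m².

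**The case against.** The strongest reply is that the section already holds the rule and the tools. The reduction below 60 carries no creatinine condition, so it covers any patient whose clearance is known. The equations are printed, calculators are linked, and height and creatinine are Day 1 studies. Section 5.4.2 likewise sets a clearance-based idarubicin reduction without ordering a clearance. The observation lists say that they cover only what the study aims need and that other studies should follow good care. Sections 4.5.3 and 4.11.3 strongly recommend an inpatient stay, so creatinine will probably be checked more often than weekly. The external guidelines and drug monographs were not available and may contain this check. ULN is not given, and at low values the gap is small or absent. Section 2.9 expects the cycle to be rare.

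Most of this stands as a limit on reach. It means that a careful site may well calculate GFR anyway, that the size of the gap is conditional, and that few patients, possibly none, will be affected. But none of it makes a site obtain the value. The idarubicin rule names no creatinine cut-off, whereas the cytarabine rule does, and a site can reasonably read that cut-off as telling it when to look. More frequent creatinine does not help a patient whose creatinine stays under the trigger.

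**Conclusion.** The concern holds, as a minor safety point. On the protocol's own text and equations, the screen for reduced clearance can miss patients whom the dose rule is meant to protect.

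The size depends on ULN. With ULN of 1.0 mg/dL or more, every height (140 to 190 cm) and every adult case examined is below 60 at the trigger. At ULN 0.5 there is no gap at 160 cm or taller and a small one at 140 cm. For a patient in the gap, the consequence is twice the daily dose that the section intends.

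The conclusion is limited to this document, because the guidelines and monographs it points to could not be read. Whether patients in the gap would be harmed also rests on a cited study that was not available.

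**What to change.** In 5.5.2, require GFR to be calculated by the printed equation for every patient before high dose cytarabine, from Day 1 creatinine and height (or age and sex from 18 years). If the estimate is below 60, or the present creatinine trigger is met, hydrate and re-determine clearance by the methods already listed, measured if possible. Apply the once-daily rule only if clearance is still below 60. Add the calculation to the required observations in 4.5.2 and 4.11.2.

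The cost is two sentences in 5.5.2 and one item in each list. Screening needs no new test and no new dose rule, because height and creatinine are already collected on Day 1. A few more patients would be hydrated and rechecked, which could delay the cycle. Some MRD-positive patients would receive half the daily cytarabine. That carries an efficacy risk, since molecular persistence after this cycle counts as an EFS event (Section 9.1) and ends protocol therapy (Section 8.1). Rechecking after hydration keeps such reductions to patients whose low clearance persists.
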